## 9 Drugs or Devices

Will the research involve drugs?

🗆 Yes 🛛 🗹 No

Will the research involve devices?

🗆 Yes 🛛 🗹 No

## 10 Study Administration

#### 10.1 Setting

- Describe the sites or locations where your research team will conduct the research. At Tufts Medical Center, HNRCA, MIRI, TMC CTRC, TMC Labor and Delivery and TMC newborn nursery. At Brigham & Women's Hospital, the BWH Research Facility, BWH Labor and Delivery and BWH Newborn Nursery.
- If the research will take place at an international site, refer to the International Guidance and International Checklist. NA
- Describe the following:
- Where research procedures will be performed.
   At Tufts Medical Center, HNRC, MIRI, TMC Labor and Delivery and TMC newborn nursery. At Dricham & Warnen's Hagnital, the DWH Bessareh Facility, DWH Labor and Delivery and DWH.

Brigham & Women's Hospital, the BWH Research Facility, BWH Labor and Delivery and BWH Newborn Nursery.

- *The composition and involvement of any community advisory board.* We will consider a community advisory board in Boston. We had such a board as part of the LIPP project in Cleveland.
- If a hospital stay will be required solely for research and if so, the expected duration of the hospital stays. NA
- If inpatients will be enrolled, clarify if study participation will require an increase in the length of hospital stay, and if so, for how long. NA
- For research conducted outside of Tufts and its affiliates: Please refer to section Multi-site Research
  - Describe the site-specific regulations/customs affecting the research
  - Describe the site-specific local scientific review and ethical review structure and procedures.
  - Describe how the study team is/will become knowledgeable of the local study site's culture, customs, regulations, and society.

## 10.2 Registration

• Describe the steps the research team will take to ensure that a subject is appropriately enrolled or registered in the study prior to receiving any study intervention (e.g. describe and submit any protocol eligibility checklist that will be used, specify who on the research team will confirm eligibility and that consent was documented, etc.).

The PI will be responsible to make sure that the subject has a thorough understanding of the research and procedure, the goals of the study and how they may be randomized into either study arm, i.e. usual care or intervention. The study coordinator will be a Master's or Bachelor's level person with research experience. They will obtain the written consent. The PI or Co-Investigator will review the study with the subject and will be available either in person or via telephone to answer any questions a potential subject may have before the subject has any evaluation

## **10.3** Resources Available

• Specify the role and tasks delegated to each research team member.

Pennington Biomedical Research Center – Research team members will perform analysis of data, and interactions with participants during recruitment, evaluation in the clinical research unit, for nutrition, and for lifestyle changes. Please see addendum for site specific procedures.

Massachusetts General Hospital & Brigham and Women's Hospital-- Potential participants will be recruited from eligible women who have delivered infants at MGH and BWH. TMC study staff will reach out by email, phone, or mail to women who agree to be contacted at a later date and will offer study participation. Consent and all subsequent study procedures will be conducted at Tufts Medical Center or

Brigham & Women's Hospital for those women who elect to participate. Cord blood and placental collection will be done according to standard of care at the respective hospitals. BWH or MGH LIPP research staff will collect designated tissue specimens from the research participant's hospital. Samples will be collected according to protocol, aliquoted and processed as needed and placed on ice or liquid nitrogen. The designated samples will either be transported to TMC/MIRI for further processing and storage by LIPP staff until analysis or processed and stored at BWH until analysis. Neonatal anthropometrics will be performed at the institution by LIPP staff and be used as an alternative measure for body fat if a PeaPod is not available. Neonatal anthropometrics may be conducted at the houses of LIPP participants with their consent if a participant delivers at a facility other than an approved LIPP study site and are unable to travel to BWH, MGH or TMC after delivery. Both anthropometrics and PeaPod will be performed otherwise. Additionally, for those participants who deliver at BWH or MGH, LIPP research staff will conduct study sample collection according to the site protocol. In addition to infant measures and study sample collection, LIPP study staff will conduct maternal questionnaires prior to delivery and post-delivery. Before delivery, the Infant Feeding Intention Scale will be conducted; after delivery, questionnaires will include the Breast-Feeding Self-efficacy after Delivery, Infant Feeding Practices Scale and the Holmes-Rahe Life Stress Inventory.

• At Tufts Medical Center;

 We will have access to subjects delivering at TMC, approximately 1300/year. To increase the likelihood of meeting our recruitment goal, we will also be recruiting at BWH, who see a higher volume of deliveries; approximately 9000/yr and 3800/yr, respectively. If recruitment is not adequate, we will explore recruiting at the other hospitals in Boston for example, BI hospital.

We are in the process of collecting demographic data from the Tufts delivery charts to determine eligibility of patients delivering at TMC.

Confirm that the amount of time you will spend on the research is adequate to conduct and complete the research.
 The PI has no clinical duties and although budgeted at 20% effort will easily spend 40 to 50% effort on the LIPP project.
 Example to the project.

Facilities HNRCA, MIRI, TMC, BWH Research Facility

- Availability of medical or psychological resources that subjects might need TMC
- Process to ensure the research team members have adequate oversight and are adequately trained regarding the protocol, study procedures, and their roles and responsibilities.
   Study staff have met once a week in Cleveland and that will continue at Tufts via telephone and Zoom conference with the PBRC and Brigham & Women's Hospital.

#### 10.4 IRB Review

- Specify that an appropriate IRB registered with the OHRP, will review and approve this study.
- Specify that any amendments to the protocol or informed consent documents will be reviewed and approved by the IRB prior to use, unless required to eliminate an apparent immediate hazard to subjects.

We have developed a DSMB to oversee the LIPP study.

We confirm that any amendments to the protocol or informed consent documents will be reviewed and approved by the IRB prior to use, unless required to eliminate an apparent immediate hazard to subjects.

#### 10.5 Multi-Site Research

Is this a multi-site study where Tufts is the sponsor, primary grant recipient, or coordinating site?

# 🗹 Yes 🛛 No

If Yes:

- Describe the processes to ensure pertinent and timely communication among sites, including:
  - When and how sites will be provided with the current version of the protocol, informed consent form, and other study documents.
     When the IBP has approved the protocol and ICE this will be provided to LIPP study staff at

When the IRB has approved the protocol and ICF this will be provided to LIPP study staff at the PBRC and BWH. The HNRCA site is functionally part of Tufts and any IRB approval for the HNRCA will go through the primary site at the MIRI.

• That all required approvals will be obtained at each site (including approval by the site's IRB of record).

This will be done before recruitment at the PBRC. At the Pennington, BWH and Tufts sites, we will recruit and follow the same protocol at each site.

 How all modifications will be communicated to sites, and will be reviewed and approved (including approval by the site's IRB of record) before the modification is implemented. We continue to have biweekly phone conference calls with staff at TMC, BWH and the Pennington. This is currently ongoing and will continue once we have IRB approval from TMC. • That all participating sites will safeguard data as required by local information security policies.

The PIs ([name] and [name]) have worked collaboratively not only on the LIPP project but also for a number of years. They have multiple projects and manuscripts where they have been co-investigators. Both are experienced and have excellent records regarding patient safety and data integrity.

- Assurance that all local site investigators will conduct the study appropriately.
  - The PIs ([name] and [name]) have worked collaboratively not only on the LIPP project but also for a number of years. They have multiple projects and manuscripts where they have been co-investigators. Both are experienced and have excellent records regarding patient safety and data integrity. The training for study staff at the Pennington has been completed as they have relocated to Baton Rouge with [name]. At BWH, [name] will ensure that all procedures will be conducted according to the study protocol. At Tufts and MGH, the study coordinator will work with the PI and Co-I regarding the study recruitment and protocol. We have a weekly telephone conference to review procedures etc.
- That all non-compliance with the study protocol or other reportable new information will be reported in accordance with local policy.
   The PI confirms that all non-compliance with the study protocol or other reportable new information will be reported in accordance with local policy.
- Describe the method for communicating the following information to participating sites:
  - Problems Weekly telephone conference calls.
  - Interim results at quarterly meetings.
  - Study closure at the time that data is analyzed and secondary analyses identified.
  - Amendments as the situations demand amendments will be made. Any changes to the protocol will be made at both sites and discussed at the weekly telephone conference.
  - Research related communications at weekly LIPP conference calls.
- Specify which site is the Data Coordinating Center. The Pennington
- Specify if Tufts' data will be shared outside of Tufts (e.g., with other investigators, sponsor, etc.) and how data will be shared.

Data will be shared with the Pennington on an ongoing basis. At the completion and publication of the study, data will be made available to other investigators per NIH guidelines.

- Describe any collaborations not described above, such as:
  - Tufts investigators with multiple affiliations that would engage other institutions in research (e.g., Tufts making direct payment to another institution for the research, the research is being conducted on behalf of another institution).

The PI has a bioscientific appointment (no salary) at MetroHealth Medical Center in Cleveland. The LIPP grant has transferred to Tufts and Tufts will be the coordinating center for the LIPP grant, [name] has percent effort on other NIH grants at Tufts as well as at other institutions. His percent effort is covered through research administration

- Each participating site will complete a Form 5 (continuing review form). The Tufts PI will collect and submit these to the Tufts Health Sciences IRB for the 2 external relying sites.
- Each participating site will complete and submit the self-audit tools to the Tufts PI, a summary of which will be submitted to the Tufts Health Sciences IRB at the time of continuing review (summary of any issues identified during the self-audit). This summary can be described in the cover letter accompanying the continuing review application. The original self-audit checklists will be available to the Tufts Health Sciences IRB upon request:
  - File Review Checklist
  - Participant File Checklist

## 10.6 Community-Based Participatory Research

Note: "Community-based Participatory Research" is a collaborative approach to research that equitably involves all partners in the research process and recognizes the unique strengths that each brings. Community-based Participatory Research begins with a research topic of importance to the community, has the aim of combining knowledge with action and achieving social change to improve health outcomes and eliminate health disparities.

Will this study involve community-based participatory research?

Not at this time, possibly at a later date

🗆 Yes 🛛 🗹 No

## 11 Addendums

11.1 Site Specific Changes: Pennington Biomedical Research Center

## Section 2.2 Risk to Subjects

- Adequacy of Protection Against Risks
  - The site PI or designee (Medical Investigator, [name], MD) will make the final decision regarding eligibility.

#### Section 4.4.1 Local Recruitment Methods

• Source of subjects (for example, patient population, local community, etc.).

- Postpartum patients at local Baton Rouge area hospitals that perform deliveries, women attending local women's health events, women responding to web- and flyer-based recruitment advertisements.
- *Methods that will be used to identify potential subjects.* 
  - Trialfacts: A web-based recruitment screening process (https://trialfacts.com/).
    - Trialfacts creates all the advertising and recruitment material used in the recruitment process, including study information pages, landing pages, prescreening questionnaires, and online advertisements. Pennington Biomedical Research Center creates an additional landing page and screening questionnaire for those that pass the Trialfacts pre-screening process.
  - Physician assisted recruitment at Baton Rouge General, whereby providers at Baton Rouge General discuss the study and handout flyers to potential participants at their discretion.
  - Posted flyers throughout the Greater Baton Rouge area in approved locations.
  - Community events
- Materials that will be used to recruit subjects.
  - Handouts, flyers, physician referrals and online screening material will be used to recruit subjects.
- When subjects respond to recruitment material, describe the information that will be provided to them about the study and the information that will be collected from subjects (e.g. name, telephone number, etc.) or submit a telephone/email script that will be used.
  - Subjects will be contacted via phone by research staff and/or directed to Pennington's Web Screener Initiator (Web screener link: https://my.pbrc.edu/Clinic/Screener/Steps/Step1).
  - If data will be retained for subjects that are determined to be ineligible, specify how privacy and confidentiality of these potential subjects will be maintained. Data will be retained until the primary manuscript is written noting differences in the study population that have determined to be ineligible for whatever reason based on inclusion/exclusion criteria.
    - Pennington Biomedical has a Notice of Privacy Practices for Protected Health Information (provided below).
- If recruitment material is being mailed or otherwise distributed, describe where/how, the distribution list will be obtained.
  - An email listserv with IRB approved information will be sent approximately every quarter to people who have subscribed to the PBRC email list.
- Specify how and why the listed recruitment methods will be effective in attracting the targeted subject population.
  - Pennington Biomedical does not provide women's health and reproductive services and as such, necessitates community involvement and hospital partnerships for recruitment. This has been successful in enrolling 12 research participants to date.

## Section 5.1 Study Design

- *Resting Energy Expenditure* 
  - Resting Metabolic Rate (RMR) will be determined after an overnight fast using a Deltatrac II indirect calorimeter (Datex-Ohmeda, General Electrics, Finland) with a canopy system.
- Neonatal Measures
  - A PEAPOD is housed at Pennington Biomedical Research Center.
  - Pennington Biomedical staff will perform requisite tissue collection at local Baton Rouge hospitals dependent on where the participant delivers (Legal agreements are provided for Baton Rouge General and Women's Hospital, while the Ochsner legal agreement is pending). After hospital discharge, participants will travel to Pennington Biomedical where a PEAPOD measure and neonatal anthropometrics will be performed. If travel is difficult, neonatal anthropometrics may be obtained at respective hospitals.

- Additionally, a medical release form will be obtained from the participant for the purpose of obtaining the antenatal chart.
- Finally, neonatal anthropometrics, caliper measurements and circumference measures may be conducted at the houses of PBRC-enrolled study participants if they are unable to travel to the PBRC site after delivery.
- Lifestyle Intervention Group
  - Supervised Exercise Intervention
    - Exercise sessions will be conducted at Pennington Biomedical Fitness Center by the Intervention Resources Department at Pennington Biomedical. (See additional descriptions below.)

#### Section 5.3 Evaluations

- All laboratory tests will be performed by the Pennington Biomedical Clinic, [name] Lab Team and/or analyzed by the Clinical Chemistry Core at Pennington Biomedical. (See additional descriptions below.)
- Sample Handling & Storage
  - Sample processing and storage will occur locally at PBRC, following the description in the parent protocol.
- Cord blood collection and placenta collection at delivery
  - This process is described in detail in our Standard Operating Procedures (SOP 2304 Placenta Collection and Processing). In brief, LIPP research staff ([name]) will collect tissue specimens from the research participant's delivering hospital. Samples will be collected according to protocol and placed on ice or liquid nitrogen. The samples will then be immediately transported by [name] to PBRC for further processing and storage by LIPP staff ([name] Lab personnel) until analysis. The clinical chemistry core will perform glucose and lipid profiles on cord blood samples. When the research participant is admitted to their delivering hospital's delivery unit, they will hand the PBRC Placental Biospecimens Delivery Unit Information sheet to the attending physician.

#### **Section 6.1 Informed Consent Process**

• The PBRC site provides additional informed consent to the infants born to enrolled mothers. This informed consent is performed with the LIPP participant at the PBRC site during the final study visit (infant measurements) or may be conducted offsite if participants are unable to travel to PBRC after delivery.

#### Interventional Resources Expertise including Facilities, Equipment, & Resource Descriptions

#### **Fitness Center**

Pennington Biomedical includes a 2300-square-foot Exercise Training Facility. The facility offers state-of the-art equipment, professional intervention technicians, and optimal training data-capturing capabilities. Staff have the ability to collect and enter data in real-time via a standing desk with dual monitors to operate the heart rate software, databases, and drive files as needed. The cardiovascular fitness training room contains 12 treadmills, 6 stationary bikes, and 2 elliptical while the strength training room has an extensive set of machines and free weights. There are 3 private rooms for intervention related counseling in a one-on-one or small group setting. For measurements, there's a private exam room complete with scale, stadiometer, and computer. In addition, there's a meeting room space capable of outfitting group exercise classes, group presentations, study orientations or introductory sessions, or childcare facility for study participants. The Fitness Center is supported by a trained staff composed of full-time exercise interventionists and students working on exercise-related degrees.

The facility is participant friendly and includes televisions, reading materials and enthusiastic staff who are well trained in customer service. Further, there are locker rooms equipped with lockers and showers available exclusively

for the use of study participants. The facility has a defibrillator, electronic scales, and multiple heart rate monitors systems (Polar and Zephr Bioharness). There is an outdoor walking track as well. The scenic walking track is 12 feet wide, paved, lighted and well-maintained. While the track is over half a mile in length there are 3 intermediate circle turn-outs that can be used to create shorter walking courses. All exercise intervention areas at Pennington are located in buildings far from the clinical assessment area with virtually no opportunity for assessment staff to accidentally observe exercising participants.

We have developed a real-time web-based system (EDIN2.0) that allows exercise interventionists to efficiently maintain accurate records of each exercise session. The progression of each participant is tracked both within individual sessions and during the entire study. Exercise can occur on a treadmill, elliptical, or cycle ergometer with the speed/grade/resistance modulated in order to keep participants at their target heart rate ( $\pm$ 3 beats) derived from the maximal exercise testing. EDIN also allows for data capture of acute energy expenditure submaximal tests and manual entries such as outdoor exercise or resistance training.

#### **Resource Descriptions**

## Exercise Interventionists & Research Specialists

Interventional Resources has 7-10 full time interventionists or specialists, and approximately 8-10 students (varied by paid, interns, and volunteer status). The Interventionists and Specialists are primarily responsible for participant contact activities which include but are not limited to conducting orientations, run-ins, collecting assessment data, physical activity or other devices, randomization assignment, and setting up and conducting the physical activity and other interventions. They are responsible for ongoing participant contact, maintaining participant records, tracking compliance and completing data entry requirements.

# 11.2 Opt-In Ancillary Studies

## 11.2.1 Breast Milk Collection

Aim: To determine the impact of the lifestyle intervention on breastfeeding outcomes and breast milk composition of the index pregnancy.

Hypothesis: Our overall hypothesis is that women randomized to the lifestyle intervention group will have higher rates of breastfeeding and less pro-inflammatory breast milk composition with a lower omega-6/omega-3 fatty acid ratio.

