#### Methods:

- **a.** Breastfeeding outcomes: Our **exposure** will be randomization group and our **outcomes** will be amount of breastfeeding versus formula feeding, duration of any breastfeeding and duration of exclusive breastfeeding. Study staff will administer validated breastfeeding outcome questionnaires every other week via text message or email to quantify duration of exclusive and any breastfeeding. Statistical analysis: We will use independent samples t-test to analyze the association between participation in the lifestyle intervention program on breastfeeding rates during each timepoint of questionnaire administration. Next, we will use multivariate logistic regression to further examine the adjusted association of lifestyle intervention with rates of breastfeeding, adjusting for key covariates.
- **b.** Breastmilk composition: Our **exposure** will be participation in the lifestyle intervention program. Our **outcomes** will be breast milk cytokines, PUFAs, leptin and insulin. Study staff will instruct mothers to collect breast milk samples and provide a 20 mL sample for this study. Participants will provide breast milk samples before initiating the intervention and then at routine study visits scheduled at 3- and 6-months following intervention initiation. If mothers indicate that they plan to stop breastfeeding based on questionnaires, we will attempt to collect a breast milk sample prior to cessation of breastfeeding. PUFAs will be measured using established methods of ultra-high performance liquid chromatography-heated electrospray ionization tandem mass spectrometry UHPLC-HESI/MS-MS. Insulin will be measured using ELISA or radioimmunoassay. For statistical analysis, we will use independent samples t-test to analyze the association between participation in the lifestyle

intervention program and the mean concentrations of these breast milk markers. We will then use multivariate logistic regression to further examine this association, adjusting for key covariates.

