**c.** Procedures: At each study visit, if a participant is still breastfeeding and consent has been signed for this ancillary sub-study, study staff will collect one 10-20mL sample of breast milk. Instructions will be provided at the previous study visit so that if desired, a participant can pump their sample at home in the morning before arrival. If the sample is provided at the study visit, participants will be asked to pump a full breast using their own pump or a disposable manual breast pump that we provide. If pumped at the visit, study staff will thoroughly mix/shake the full sample and pour 10-20ml into the provided sterile container; if at home, the participant will be given instructions on how to prepare the sample. The remainder of the sample will be returned to the subject. This sample will be carried by the BWH LIPP study staff to BWH where they will be stored in freezers in a secured room in a secured building by subject ID number and date of collection to be used for future analysis.

The impact of the proposed supplemental work lies in identifying modifiable factors that may impact breastfeeding outcomes, offspring growth and adiposity. Results from this study could provide further insight into the role of lactational programming in intergenerational obesity.

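### Ancillary breast-milk study: the predicted fall in the omega-6/omega-3 ratio has no planned test, because the milk analyses compare mean concentrations only

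*Combined protocol and SAP*

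**What the plan says.** Section 11.2.1 (Breast Milk Collection) describes an opt-in ancillary study of milk from the index pregnancy. Its hypothesis has two parts. The first is that "women randomized to the lifestyle intervention group will have higher rates of breastfeeding". The second is "less pro-inflammatory breast milk composition with a lower omega-6/omega-3 fatty acid ratio".

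Methods a analyses breastfeeding rates. Methods b covers milk composition:

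- The outcomes are "breast milk cytokines, PUFAs, leptin and insulin".
- The first analysis is an independent-samples t-test on "the mean concentrations of these breast milk markers".
- The second reads: "We will then use multivariate logistic regression to further examine this association, adjusting for key covariates".
- Samples are taken before the intervention starts and at 3 and 6 months after it starts. An extra sample is attempted if a mother plans to stop breastfeeding.
- PUFAs are assayed by liquid chromatography with tandem mass spectrometry. No unit is given, and no normalisation to milk fat or to total fatty acids is mentioned.

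The procedures in part c ask for a full breast to be expressed when milk is pumped at the visit, after which "study staff will thoroughly mix/shake the full sample and pour 10-20ml into the provided sterile container". Home samples are allowed, prepared from instructions whose content is not described.

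Section 11.2.1 gives no sample size, effect size, standard deviation or power for the milk analyses.

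**The concern.** The ratio is the only specific quantity in the milk part of the hypothesis, yet it is not an outcome, a derived variable or a tested quantity in Methods b or in the procedures. An analyst who followed the section exactly would report differences in separate marker means and nothing on the ratio.

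A ratio analysis could be added later. By then, the choice of fatty acids in the numerator and denominator, the scale, and which of the follow-up samples counts would all be open after the data had been seen.

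A second, conditional issue concerns the PUFAs alone. If they are reported per volume of milk, total fat in the sample moves omega-6 and omega-3 up and down together. That variation cancels in the ratio, or in shares of total fatty acids, but stays in each concentration.

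**Working it through.** **1. Hypothesis against analysis**

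| Element of the hypothesis | Outcome listed | Planned analysis |
|---|---|---|
| Higher breastfeeding rates | Yes, Methods a | t-test, then logistic regression |
| Less pro-inflammatory milk | Yes, cytokines in Methods b | t-test on means, then logistic regression |
| Lower omega-6/omega-3 ratio | No; PUFAs only | None on the ratio |

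The logistic step does not close the gap. It examines the same association with the same continuous markers, and no cut-point is given that would make them binary.

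**2. Why two separate mean comparisons do not test the ratio**

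Two cases show it:

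- Both families fall by 20%. Each mean changes, but the ratio changes by a factor of 0.80/0.80 = 1, so not at all.
- Omega-6 falls 7% and omega-3 rises 10%. The ratio changes by 0.93/1.10 = 0.845, a fall of about 15%, although each single change is modest.

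A difference in either mean therefore neither establishes nor excludes a difference in the ratio.

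**3. Illustration of size**

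There is no figure in the plan to reproduce. Every input here is an assumption: two-sided alpha 0.05, 30 women per arm, a true ratio 20% lower, log-SD of each fatty acid share 0.2, shares independent, and log-SD of total milk fat (s) from 0 to 0.5.

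- Model: log concentration = log fat + log share.
- Effect on the log ratio: |ln 0.8| = 0.223. If split evenly, each family shifts by 0.112.
- SD of the log ratio: √2 × 0.2 = 0.283, whatever s is.
- SD of a log concentration: √(s² + 0.2²).
- Power ≈ Φ(effect / (SD × √(2/n)) − 1.96).

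Worked case at s = 0.4:

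- Ratio: 0.223 / (0.283 × 0.258) = 3.06, so power is Φ(1.10) ≈ 86%.
- One concentration, even split: SD = √(0.16 + 0.04) = 0.447, and 0.112 / (0.447 × 0.258) = 0.97, so power is Φ(−0.99) ≈ 16%.

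| s | Log ratio | Each concentration, even split | Omega-3 concentration, whole change in omega-3 |
|---|---|---|---|
| 0 | 86% | 58% | 99% |
| 0.2 | 86% | 33% | 86% |
| 0.3 | 86% | 22% | 67% |
| 0.4 | 86% | 16% | 49% |
| 0.5 | 86% | 12% | 36% |

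Simulated t-tests at s = 0.4 with the even split, using raw omega-3 concentration and the log ratio, gave 14% and 86%.

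A wider simulated grid used omega-6 −7% and omega-3 +10%, milk-fat CV 20% to 50%, share log-SD 0.15 to 0.25, and 25 to 40 women per arm. Concentration tests had 7% to 39% power and the log-ratio test 37% to 94%.

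**4. If milk fat differed by arm**

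Suppose there is no true change in the ratio, but fat is 20% higher in one arm (30 per arm, share log-SD 0.2). The shift is ln 1.2 = 0.182.

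- At s = 0.2: 0.182 / (0.283 × 0.258) = 2.50, so a concentration test is significant Φ(0.54) ≈ 70% of the time.
- At s = 0.4: 0.182 / (0.447 × 0.258) = 1.58, so Φ(−0.38) ≈ 35% of the time.
- The ratio test stays at 5% in both.

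**The case against.** The strongest reply is that this is a wording gap in an opt-in ancillary study. PUFAs are assayed, so the ratio can be derived from planned data. The other elements of the hypothesis do have analyses: breastfeeding rates under Methods a, and cytokines for the inflammatory element under Methods b. All of that stands. A reader might infer that the hypothesis as a whole goes untested, but the documents do not support that; only the ratio prediction lacks a test. Being able to derive a variable does not pre-specify it, so the reply narrows the point without removing it.

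A reader might also infer that all the milk tests depend on how fatty each sample is. The documents do not support that either. They give no unit for PUFAs and no basis for extending the argument to cytokines, leptin or insulin. Even for PUFAs it is an inference that holds if they are expressed per volume.

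Nor does fat variation by itself create a false finding. Between randomised arms it is noise that costs power. It misleads only if fat or sampling differs by arm, and nothing in the protocol says the intervention changes milk fat. Full-breast expression and mixing at the visit reduce variation within one expression, though not between women, and home samples are less controlled.

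Finally, the power advantage of the ratio depends on the assumed pattern. If the whole change is in omega-3 and milk fat varies little, the omega-3 concentration test equals the ratio test (86% each at s = 0.2) or beats it (99% against 86% at s = 0). It cannot be said that a real change in the ratio would generally be missed.

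**Conclusion.** The point holds for the ratio. Section 11.2.1 predicts a lower omega-6/omega-3 ratio and plans no analysis of it; neither the t-tests on means nor the logistic regression fills the gap. This rests on the text alone and needs no assumption.

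The milk-fat argument is secondary and conditional on PUFAs being expressed per volume. The power figures are illustrations on assumed inputs. They show that the choice of outcome can matter a good deal, not how much power this sub-study has.

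The change is worth making because it gives the one specific milk prediction a defined test at almost no cost. The breastfeeding and cytokine elements and the trial's primary outcome, neonatal adiposity, are unaffected.

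**What to change.** In section 11.2.1, Methods b:

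- Name the log omega-6/omega-3 ratio at one stated post-initiation visit as the milk PUFA outcome. Say whether a sample taken before stopping breastfeeding may stand in for that visit.
- Define which fatty acids enter the numerator and the denominator.
- Compare the log ratio by randomised group with linear regression, adjusted for the log ratio in the pre-intervention sample already being collected. Replace the logistic regression for the other continuous milk markers with linear regression too.
- Report individual PUFAs as a share of total measured fatty acids, or state the unit.
- Keep cytokines as the outcome for the inflammatory element of the hypothesis.

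The cost is wording and minor analysis work. The ratio comes from the PUFA assay already planned, and no new samples or visits are needed.
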